2.1 SAFETY OBJECTIVE

The primary objective for this study is as follows:

- To evaluate the safety and tolerability of cobimetinib in children and young adults, including estimation of the MTD or the maximum administered dose (MAD) and characterization of dose-limiting toxicities (DLTs)

2.2 PHARMACOKINETIC OBJECTIVE

The PK objective for this study is as follows:

- To characterize the PK of cobimetinib in children and young adults

2.3 EFFICACY OBJECTIVE

The efficacy objective for this study is as follows:

- To evaluate the anticancer activity of cobimetinib in children and young adults with solid or brain tumors, as measured by objective response rate (ORR), progression-free survival (PFS), duration of objective response (DOR), and OS

2.4 DOSE-FINDING OBJECTIVE

An additional objective for this study is as follows:

- To identify recommended Phase II doses for cobimetinib tablet and suspension formulations in pediatric patients on the basis of safety, PK, and efficacy outcome measures (see Section [3.4](#))

2.5 EXPLORATORY OBJECTIVES

The exploratory objectives for this study are as follows:

- To explore the relationship between cobimetinib exposure and changes in levels of pharmacodynamic (PD) biomarkers in children and young adults
- To explore non-inherited biomarkers that may be predictive of response to cobimetinib (i.e., predictive biomarkers), may be associated with progression to a more severe disease state (i.e., prognostic biomarkers), acquired resistance to cobimetinib, or susceptibility to developing adverse events, may provide evidence of cobimetinib activity, or may increase the knowledge and understanding of disease biology
- To explore inherited biomarkers (i.e., variants in germline DNA) that may be predictive of response to cobimetinib (i.e., predictive biomarkers), may be associated with progression to a more severe disease state (i.e., prognostic biomarkers), acquired resistance to cobimetinib, or susceptibility to developing adverse events, or may increase the knowledge and understanding of disease biology
- To explore potential relationships between PK parameters for cobimetinib and other outcome measures (such as safety or efficacy outcome measures)
- To evaluate tumor characteristics before and after treatment on the basis of available magnetic resonance imaging (MRI) and positron emission tomography (PET) scans
- To evaluate specific aspects of the acceptability of the cobimetinib formulations

3. STUDY DESIGN

3.1 DESCRIPTION OF STUDY

This is a Phase I/II, multicenter, open-label, dose-escalation study designed to evaluate the safety, tolerability, PK, and preliminary efficacy of cobimetinib in pediatric and young adult patients with solid tumors with known or potential RAS/RAF/MEK/ERK pathway activation for which standard therapy has proven to be ineffective (i.e., relapsed or refractory tumors) or intolerable or for which no curative standard-of-care treatment options exist.

Patients will be enrolled via an interactive web response system (IWRS) in two stages: a dose-escalation stage and an expansion stage at the recommended dose. During the dose-escalation stage, cohorts of 3–6 pediatric patients (age ≥ 6 months to < 18 years) will be evaluated at escalating dose levels to determine the MTD or MAD of cobimetinib in pediatric patients with advanced solid tumors. The MTD or MAD of each cobimetinib formulation (tablet and suspension) will be determined in separate dose escalations (as described in Section 3.1.1). Once the MTD or MAD has been established, pediatric patients (age ≥ 6 months to < 18 years) will be enrolled in the expansion stage and treated at the recommended dose, which will be at or below the MTD or MAD, as determined by the Sponsor; adult patients ≥ 18 years of age with pediatric tumor types

can be enrolled on this study but only during the expansion stage; these adult patients will be treated at the adult flat dose (see Section 3.1.2). Approximately 70 patients are expected to be enrolled in the dose-escalation and initial expansion stages of this study, at approximately 30 investigative sites in Europe and North America. If an efficacy signal is observed during the first expansion step for the initial response assessment, up to an additional 30 patients per cohort may be enrolled in the second expansion step for the additional response assessment.

All patients will be closely monitored for adverse events throughout the study and for at least 30 days after the last dose of study treatment (see Section 5.3.1). Adverse events will be graded according to the National Cancer Institute Common Terminology Criteria for Adverse Events (NCI CTCAE), v4.0. Other safety assessments include echocardiograms, ophthalmologic examinations, and dermatologic examinations.

To characterize the PK properties of cobimetinib, blood samples will be taken at defined timepoints after dosing (see Appendix 2).

Tumor assessments will be performed in the final week of every other cycle, starting with Cycle 2 (see Section 4.5.5 for more information). Response will be determined by the investigator using the modified International Neuroblastoma Response Criteria (mINRC) for patients with neuroblastoma (see Appendix 3), Response Assessment in Neuro-Oncology (RANO) criteria for patients with HGG (see Appendix 4), RECIST v1.1 (see Appendix 6) for patients with other tumors, and RANO criteria for patients with low-grade glioma (LGG; see Appendix 5) in the expansion stage in addition to RECIST v1.1.

Patients in both dose-escalation and expansion stages will receive cobimetinib orally according to the guidance provided in Appendix 10 on Days 1–21 of each 28-day treatment cycle (21/7 dosing schedule) until the occurrence of disease progression as determined by the investigator, death, unacceptable toxicity, or patient or investigator decision to discontinue treatment.

The schedule of assessments is provided in Appendix 1 and the schedule of PK and PD assessments is provided in Appendix 2.

3.1.1 Dose-Escalation Stage

Cohorts of 3–6 pediatric patients each will be treated at escalating doses of cobimetinib in accordance with the dose-escalation rules described below. The first patient at each dose level must complete at least 5 days of treatment (Days 1–5 of Cycle 1) without a DLT (as defined in Section 3.1.1.1) before subsequent patients can be treated at the same dose level.

The DLT assessment window is defined as Days 1–28 of Cycle 1. Adverse events identified as DLTs, as defined below (see Section 3.1.1.1), will be reported to the Sponsor within 24 hours (see Section 5.4.2).

[figure not shown]
Two formulations will be available for the protocol: a tablet (20 mg) and a suspension (4.8 mg/mL). An MTD or MAD will initially be determined for tablets in patients 6 years and above. Once the MTD or MAD is identified for tablets, enrollment of patients using the suspension will commence following review of relevant data from the tablet dose escalation. The starting dose for the suspension will be a minimum of one dose level below the MTD or MAD of the tablets (see Section 3.1.1.2 for age requirements for suspension). Additional dose escalation with the suspension may proceed according to the dose escalation rules (Section 3.1.1.2) until an MTD or MAD is identified for the suspension. On the basis of an ongoing review of safety data and available PK data, increases in dose level or continued enrollment for either formulation may be halted by the Sponsor as deemed appropriate.

Patients who discontinue from the study prior to completing the DLT assessment window for reasons other than a DLT will be considered non-evaluable for dose-escalation decisions and MTD or MAD assessments. These patients will be replaced at that same dose level unless there are 3 or more patients already treated and all were evaluated with no DLT at that level. Patients who miss five or more doses (i.e., > 18% of the cumulative dose) during the DLT assessment window for reasons other than toxicity will also be replaced. Patients who ingest moderate or strong CYP3A inducers or inhibitors (defined in Appendix 11), ingest prohibited foods/supplements (defined in Section 4.4.3), or receive supportive care during the DLT assessment window that confounds the evaluation of DLTs (not including supportive care described below as part of the DLT definition) may be replaced at the discretion of the Medical Monitor.

Patients who experience a DLT during the assessment window (first 28 days) may not subsequently continue drug at full dose, even if the drug is withheld until resolution of the toxic event. The investigator should use guidance in Section 5.1.1 and Table 2 (and if guidance is not specified, investigator discretion) to determine whether the patient should permanently discontinue study drug or withhold study drug until toxicity resolves to Grade 1 or lower, then resume study drug at a dose corresponding to a reduction of one dose level.

A study schema for the dose-escalation stage is displayed in Figure 1.

Figure 1 Study Schema: Dose-Escalation Stage

DLT = dose-limiting toxicity.

Note: All patients will receive cobimetinib orally once daily on Days 1–21 of each 28-day cycle. Dose escalation for suspension will proceed in the same way after MTD of tablets has been established, starting at one dose level below the determined MTD or MAD of the tablets, and allowing for enrollment of patients 6 months to 6 years of age as permitted in Section 3.1.1.2.

3.1.1.1 Definition of Dose-Limiting Toxicity

Any one of the following events will be considered a DLT if it occurs during the DLT assessment window and is assessed by the investigator to be related or possibly related to cobimetinib (rules for attributing causality are defined in Section 5.3.4):

- Grade ≥ 4 neutropenia (ANC $< 0.5 \times 10^9/L$) lasting > 7 days
- Grade ≥ 4 neutropenia with documented infection
- Febrile neutropenia, defined as ANC $< 500/mm^3$ with a single temperature of $> 38.3^\circ C$ ($101^\circ F$) or a sustained temperature of $\geq 38^\circ C$ ($100.4^\circ F$) for more than 1 hour
- Grade ≥ 4 (i.e., life threatening) anemia of any duration

- Grade ≥ 4 thrombocytopenia lasting > 48 hours or any thrombocytopenia requiring a platelet transfusion, with the following exception:
 - For patients who have undergone autologous stem cell transplant or ^{131}I -metaiodobenzylguanidine (MIBG) therapy, Grade ≥ 4 thrombocytopenia lasting > 7 days or any thrombocytopenia requiring a platelet transfusion on two or more separate dates will be considered a DLT.
- Grade ≥ 3 thrombocytopenia with bleeding
- Elevation of serum hepatic transaminase (ALT or AST) $\geq 5 \times$ the upper limit of normal (ULN)
 - For patients with elevated hepatic transaminase levels at baseline as a result of liver metastases, hepatic transaminase $\geq 5 \times$ baseline and $< 10 \times$ baseline for > 3 days, or any hepatic transaminase $\geq 10 \times$ baseline, will be considered a DLT.
- Elevation of serum bilirubin $\geq 3 \times$ ULN
- For patients reliably able to report visual symptoms: Grade ≥ 2 visual disturbance that does not resolve to Grade ≤ 1 within 72 hours after interruption of cobimetinib treatment
- Retinal pathology of any grade, or Grade ≥ 2 uveitis or iritis
- Grade ≥ 2 hemorrhage of any type
- Intracranial hemorrhage of any grade
- Grade ≥ 4 CPK elevation
- Rhabdomyolysis of any grade
 - Rhabdomyolysis includes elevations of CPK in conjunction with either clinical features (such as muscle pain, signs of renal failure, dark red or brown urine) or with laboratory evidence of renal insufficiency (including Grade 2 or higher increased creatinine or creatinine clearance [or radioisotope glomerular filtration rate] < 70 mL/min/1.73 m²), or investigator judgment that a clinical scenario is consistent with rhabdomyolysis.
- Grade ≥ 2 ventricular dysfunction or symptomatic congestive heart failure
- Reduction in left ventricular ejection fraction (LVEF) below 50% (or shortening fraction below 28%) AND either symptomatic heart failure or a $\geq 10\%$ relative reduction from baseline measurement
 - Note: The relative reduction must be $\geq 10\%$ of baseline function, not an absolute decrease of ≥ 10 percentage points.
- Grade ≥ 4 (i.e., life threatening) vomiting or diarrhea of any duration

- Grade ≥ 3 non-hematologic, non-hepatic, non-ocular adverse event, with the following exceptions, which will not be considered DLTs:
 - Grade ≥ 3 diarrhea or rash that resolves to Grade ≤ 2 within 7 days after interruption of cobimetinib treatment.
 - Grade 3 fever.
 - Grade 3 mucositis or stomatitis that resolves to Grade ≤ 2 within 3 days.
 - Grade ≥ 3 nausea or vomiting that responds to standard-of-care therapy within 3 days.
 - Grade 3 fatigue lasting ≤ 3 days.
 - Grade 3 laboratory abnormalities that are asymptomatic and considered by the investigator not to be clinically significant.

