Female patients must remain abstinent or use single or combined contraceptive methods that result in a failure rate of $< 1\%$ per year during the treatment period and for at least 3 months after the last dose of study drug. Female patients must refrain from donating eggs during this same period.

True abstinence is only acceptable if it is in line with the preferred and usual lifestyle of the patient. Periodic abstinence (e.g., calendar, ovulation, symptothermal, or postovulation methods) and withdrawal are not acceptable methods of contraception.

Examples of contraceptive methods with a failure rate of $< 1\%$ per year include, hormonal implants, established, proper use of combined oral or injected hormonal contraceptives, and certain intrauterine devices. Alternatively, two methods (e.g., two barrier methods such as a condom and a cervical cap) may be combined to achieve a failure rate of $< 1\%$ per year. Barrier methods must always be supplemented with the use of a spermicide.

- For male patients with a female partner of childbearing potential or a pregnant female partner: Agreement to remain abstinent or use a condom during the treatment period and for at least 3 months after the last dose of study drug
 - True abstinence is only acceptable if it is in line with the preferred and usual lifestyle of the patient. Periodic abstinence (e.g., calendar, ovulation, symptothermal, or postovulation methods) and withdrawal are not acceptable methods of contraception.
- For male patients: agreement to refrain from donating sperm during the treatment period and for at least 3 months after the last dose of study drug
- Adequate hematologic and end organ function, defined by the following laboratory results obtained within 28 days prior to initiation of study drug:
 - ANC $\geq 0.75 \times 10^9/L$ (unsupported)
 - Platelet count $\geq 75 \times 10^9/L$ (unsupported)
 - Hemoglobin ≥ 8 g/dL (transfusion is acceptable to meet this criterion)
 - Bilirubin $\leq 1.5 \times ULN$ for age
 - AST and ALT $\leq 2.5 \times ULN$ for age
 - Serum creatinine $\leq 1.5 \times ULN$ for age or creatinine clearance (or radioisotope glomerular filtration rate) > 70 mL/min/1.73 m²
- Fractional shortening (FS) $\geq 30\%$ and LVEF $\geq 50\%$ at baseline, as determined by echocardiography or multigated acquisition scan (MUGA) within 28 days prior to initiation of study drug

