5.1.1 Management of Specific Adverse Events

Guidelines for managing specific adverse events are provided in [Table 2](#). Asymptomatic declines in left ventricular ejection fraction should be managed according to the algorithm presented in [Table 3](#) in Section [5.1.2.1](#).

If dose reduction is indicated for an individual patient, the dose should be reduced to the next lower dose level, with dose defined in [Appendix 10](#). The dose regimen of adult patients (≥ 18 years of age) treated with the adult-recommended daily dose of 60 mg will be reduced by one 20 mg tablet (i.e., from 60 mg to 40 mg). If the patient is treated at the lowest defined dose level, the dose should be reduced by 25%. Note that the need for dose reduction below the minimum doses for administration in this study (specified in [Appendix 10](#)) is considered unacceptable toxicity and requires study drug discontinuation. For patients taking tablets, study drug should be discontinued if required weekly dose after reduction is < 60 mg/week. For patients taking suspension, study drug should be discontinued if required dose after reduction is < 4.8 mg (1 mL) daily. Dose re-escalation is not allowed.

Table 2 Guidelines for Management of Specific Adverse Events

Event	Action to Be Taken

Grade ≥ 2 diarrhea
	
Grade ≥ 3 diarrhea
 
 • If Grade ≥ 3 diarrhea occurs despite adequate supportive care, do not administer cobimetinib until recovery to Grade ≤ 1. • Following recovery, resume cobimetinib at a dose corresponding to a reduction of one dose level. • If patient experiences two episodes of Grade ≥ 3 diarrhea despite adequate supportive care, discontinue cobimetinib permanently. 
Grade 2 diarrhea
 
 • If Grade 2 diarrhea persists for ≥ 10 days despite adequate supportive care, do not administer cobimetinib until recovery to Grade ≤ 1. • Following recovery, resume cobimetinib at a reduced dose after consulting with the Medical Monitor.

Any rash with concurrent signs or symptoms strongly suggestive of a severe Type I hypersensitivity or anaphylactic or anaphylactoid reaction, with painful desquamation or mucosal involvement suggestive of Stevens-Johnson syndrome or toxic epidermal necrolysis, or with other life-threatening complications
	
 • Discontinue cobimetinib permanently. • Immediately consult a dermatologist.

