
Skin lesion suspicious for SCC/BCC
	
 • Do not administer cobimetinib. • Immediately consult a dermatologist. • Biopsy suspicious lesions. If lesion is benign, resume cobimetinib; if lesion consistent with SCC or BCC, do not resume cobimetinib.

Table 2 Guidelines for Management of Specific Adverse Events (cont.)

Event	Action to Be Taken

Grade ≥ 3 rash that does not meet above criteria
	
 • Consult a dermatologist. • Do not administer cobimetinib until recovery to Grade ≤ 2. • Following recovery, resume cobimetinib at a dose corresponding to a reduction of one dose level. • If patient experiences two episodes of Grade ≥ 3 rash, discontinue cobimetinib. • If Grade ≥ 3 rash persists for > 10 days despite adequate supportive care, discontinue cobimetinib permanently.

Retinopathy or Grade ≥ 2 visual disorders
	
 • Do not administer cobimetinib. • Consult ophthalmologist, who should perform complete ophthalmologic examination that includes visual acuity testing, IOP measurements by tonometry, slit-lamp ophthalmoscopy, indirect ophthalmoscopy with dilation, and SD-OCT. • Resume cobimetinib if no evidence of retinopathy and either visual disorder has recovered to Grade ≤ 1 or visual disorder is attributable to underlying disease (i.e., optic glioma). 
Diagnosis of serous retinopathy
 
 • Do not administer cobimetinib until retinopathy has resolved (or in patients who were symptomatic at presentation, recovered to Grade ≤ 1). • When retinopathy resolves, resume cobimetinib at the next lower dose per the dose-escalation scheme, or if at or below lowest dose level, reduce dose by 25% (Section 3.1.1.2). • If retinopathy recurs, discontinue cobimetinib permanently. 
Diagnosis of retinal vein occlusion or Grade 3+ retinal detachment
 
 • Permanently discontinue cobimetinib

Grade ≥ 3 ALT or AST elevations
	
ALT or AST elevation of $\geq 5 \times$ ULN
 
 • Do not administer cobimetinib until recovery to $< 3 \times$ ULN. • Following recovery, resume cobimetinib at a dose corresponding to a reduction of one dose level. 
ALT or AST $> 3 \times$ ULN in combination with total bilirubin $> 2 \times$ ULN or clinical jaundice
 
 • Discontinue cobimetinib permanently.

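### The DLT list in Section 3.1.1.1 has no combined hepatic criterion, so an early Hy's law event below both single-analyte limits is left out of the dose-escalation count; one bullet would largely close the gap

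*Combined protocol and SAP*

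**What the plan says.** **What counts as a DLT (3.1.1.1).** The event must fall in Days 1–28 of Cycle 1 and be judged related or possibly related. There are two separate hepatic items: ALT or AST of at least 5 x ULN, and "Elevation of serum bilirubin $\geq 3 \times$ ULN". A sub-item begins "For patients with elevated hepatic transaminase levels at baseline as a result of liver metastases" and moves the transaminase limit to multiples of baseline: 5 to below 10 x baseline for more than 3 days, or 10 x baseline or more at any time. The general Grade 3 item covers only a "non-hematologic, non-hepatic, non-ocular adverse event", so it cannot pick up a liver event.

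**How the combination is treated elsewhere.** Section 5.3.5.6 takes ALT/AST above 3 x ULN together with bilirubin above 2 x ULN, or jaundice, as indicating severe liver injury when cholestasis and other explanations are absent. Section 5.2.3 makes it an adverse event of special interest, reportable within 24 hours. In Table 2 (5.1.1), the line containing "ULN in combination with total bilirubin" directs permanent discontinuation, but it sits under the row heading "Grade ≥ 3 ALT or AST elevations".

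**How an early stop is counted.** A child who stops drug in the window for a non-DLT reason is replaced (4.6.2), unless at least 3 patients at that level have been treated and all were evaluated without a DLT (3.1.1). Two DLTs among the first six evaluable patients mean the MTD is exceeded (3.1.1.2).

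**The concern.** Characterizing DLTs and estimating the MTD are part of the primary objective. The rule that produces the MTD does not see one form of liver injury that the protocol itself singles out as severe. If drug is stopped, the event leaves both numerator and denominator. If the investigator continues drug, which Section 5.1 leaves room for, the child counts as DLT-free. Either way the omission acts in one direction only, toward escalation, in a paediatric trial. Other composite toxicities are already on the list (neutropenia with infection, thrombocytopenia with bleeding, CPK with clinical or renal signs); the liver has none.

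**Working it through.** **1. The plan's own figure.** 2/6 = 33.3%, so fewer than 2 of 6 agrees with the limit of under 33% in Section 3.1.1.2.

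**2. Where the gap lies.** A DLT needs ALT/AST ≥ 5 x ULN or bilirubin ≥ 3 x ULN; the combined event needs ALT/AST > 3 x ULN and bilirubin > 2 x ULN. A grid in steps of 0.1 x ULN finds points that meet the second and not the first only at ALT/AST 3.1–4.9 and bilirubin 2.1–2.9 x ULN. Jaundice with bilirubin below 3 x ULN adds to this. A case that later crosses either single-analyte limit inside the window is counted.

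**3. The Table 2 ambiguity.** If the row text governs, the whole band carries a mandated stop. If the row heading governs, the mandated stop largely starts where the 5 x ULN DLT item does, since the other line in that row also begins at 5 x ULN.

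**4. Liver metastases: a gap on either reading.** Eligibility allows "AST and ALT $\leq 2.5 \times ULN$ for age" and the DLT limit starts at 5 x baseline, so it can sit as high as 5 x 2.5 = 12.5 x ULN. Example: baseline 2 x ULN, then ALT 9 x ULN (9/2 = 4.5 x baseline) with bilirubin 2.5 x ULN. This falls in the Table 2 row however it is read, and is not a DLT.

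**5. Effect on the Table 1 decision.**
- One listed DLT plus one such case, replaced by a clear patient, reads as 1/6 (dose increase). Scored, it is 2/6 (MTD exceeded).
- Three clear patients plus one such case reads as 3/3 with no replacement (dose increase). Scored, it is 1 DLT in 4 enrolled (same dose).

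**6. Average size.** Let p be the listed-DLT rate and h the rate of the uncounted event, excluding cases that later cross a listed limit and taking the two as mutually exclusive. The documents give neither, so both are assumptions. As written, with replacement, the effective rate is r = p/(1−h); if scored, r = p+h. For six evaluable patients, P(at most 1 DLT) = (1−r)^6 + 6r(1−r)^5.

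Worked line, p = 20% and h = 1%: r = 0.2/0.99 = 0.2020 gives 65.0%; r = 0.21 gives 63.1%; the difference is 2.0 points.

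| h | p = 10% | p = 20% | p = 30% | Difference (points, before rounding) |
|---|---|---|---|---|
| 0.5% | 88.5 vs 87.6 | 65.3 vs 64.3 | 41.7 vs 40.9 | 0.7–1.0 |
| 1% | 88.4 vs 86.6 | 65.0 vs 63.1 | 41.4 vs 39.9 | 1.5–2.0 |
| 2% | 88.2 vs 84.4 | 64.5 vs 60.6 | 40.7 vs 37.8 | 2.9–3.9 |

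(Percent; as written vs scored.)

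If drug is continued and the child counts as clear, r = p as written, and the differences become 1.0–1.2 points (h = 0.5%) and 2.0–2.5 points (h = 1%). On a simplified path that escalates on 3/3 or otherwise goes to six, (1−r)^3 + 3r(1−r)^5, the replacement case gives 0.7–0.9 and 1.4–1.7 points. The exact rolling-6 value depends on accrual timing.

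**7. What a larger effect would need.** With replacement, a 5-point change requires h of about 2.6% (p = 10% or 20%) or 3.6% (p = 30%). Section 5.1.2.2 reports no Grade 3 or higher liver test elevation on adult monotherapy except one Grade 3 bilirubin increase. That does not measure this band, but it points low.

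**The case against.** **A stop trigger need not be a DLT.** The protocol separates the two elsewhere. Two episodes of Grade 3 or higher "diarrhea despite adequate supportive care, discontinue cobimetinib permanently", while Grade 3 or higher "diarrhea or rash that resolves to Grade" 2 or lower within 7 days of interruption is exempt from the DLT list. This stands. A reader might infer that the protocol contradicts itself because a permanent-stop event is not a DLT; the diarrhea rules show that the documents do not support that.

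**The event is rare and visible.** It reaches the Sponsor within 24 hours. Adverse event and laboratory data are reviewed before each escalation decision, the Sponsor may halt increases (3.1.1.2), the IMC recommends the expansion dose (3.1.3), and that dose is at or below the MTD or MAD (3.1.2). This also stands, and it makes the figures above upper bounds on wrong escalation at the assumed rates. These safeguards are discretionary, however, and none alters the count.

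**Conditional figures can mislead.** Given one such case among six, the chance that one listed DLT occurs in the other five and the replacement is clear is 5p(1−p)^5: 30%, 33% and 25% at p = 10%, 20% and 30%. A reader might infer that a quarter to a third of decisions are at risk. They are not: at h = 1% the chance of any such case in six is 1 − 0.99^6 = 5.9%, and 5.9% x 33% is about 2%.

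**A combined bullet can over-count.** Eligibility allows ALT/AST up to 2.5 x ULN and bilirubin up to 1.5 x ULN. A child at both ceilings without liver metastases would reach the new limits with rises above 3/2.5 = 1.2-fold and 2/1.5 = 1.33-fold. This is a real cost, limited by the relatedness condition and by excluding other explanations.

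**Conclusion.** The gap is in the text and is bounded as in step 2 of the working, with a wider form for children with liver metastases. For the main band, the mandated stop depends on whether the Table 2 row text or its heading governs; that the event is not scored does not. The effect on the MTD decision is small, about 1–2 points at assumed event rates of 0.5–1% and listed-DLT rates of 10–30%, before the safeguards. Nothing in the documents supports the rates of 2.6% or more that a 5-point change would need. A reader might infer that the MTD rule is unsound; the documents do not support that. The finding is a cheap improvement: the omission always favours escalation, it concerns an event the protocol itself regards as severe, and closing most of it takes one line. Confidence is high that the gap exists. Its size rests on assumed rates.

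**What to change.** Add one bullet to Section 3.1.1.1, under the existing related or possibly related condition:

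> *ALT or AST > 3 x ULN with total bilirubin > 2 x ULN or clinical jaundice, where there is no cholestasis and no other explanation for the raised bilirubin (Section 5.3.5.6). Where liver metastases had already raised the transaminases at baseline, use ALT or AST > 3 x baseline with the same bilirubin or jaundice limits; liver metastases present at baseline do not by themselves count as another explanation.*

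Leave Table 2 and the replacement rules unchanged.

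Say openly that the liver-metastasis clause narrows the gap without closing it: values between 3 x ULN and 3 x baseline (up to 3 x 2.5 = 7.5 x ULN) stay uncounted. The example in step 4 of the working would be caught (limit 3 x 2 = 6 x ULN, observed 9). A child with baseline 2.5 x ULN, ALT 7 x ULN (2.8 x baseline) and bilirubin 2.5 x ULN would not.

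Cost: a slightly more conservative MTD and occasional over-counting near the eligibility ceilings. No extra patients, visits or tests are needed, because ALT, AST, fractionated bilirubin and alkaline phosphatase are already in the chemistry panel (4.5.9). The change needs approval as an amendment (9.6), which should state how dose levels already cleared under the present definition are treated.
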